## 6. MILESTONES

Milestone	Planned Date
IRB/IEC approval	Jun 2021
Start of data collection	Jul 2021
End of data collection	Aug 2021
Final report of study results:	Dec 2021

## 7. RATIONALE AND BACKGROUND

Diabetes has been a major public health concern all over the world. According to the data from the IDF Diabetes Atlas 2017, there are now around 425 million adults aged 20-79 worldwide living with diabetes. In China, the prevalence of diabetes among adults was 10.9%, representing an estimated 114.4million Chinese adults with diabetes. The mortality among patient with diabetes was high, which estimated that 4 million adults died from diabetes worldwide in 2017. And diabetes has become a worrying burden upon the world's healthcare system recently. Studies have shown that the global health expenditure attributed to diabetes was estimated at USD 673 billion in 2015 and has risen to USD 727 billion 2017.

The heavy disease burden is mainly due to diabetic complications. Diabetes is a major risk factor for cardiovascular disease (CVD) and chronic kidney disease (CKD). The prevalence of CVD and CKD among patients with diabetes was high. Study suggested that diabetic kidney disease developed in up to 50 percent of diabetic patients at 20 years after a diabetes diagnosis, with 15 percent having progressed to end stage renal disease (ESRD) by this time. In the INTERHEART study, diabetes accounted for 10 percent of the population-attributable risk of a first myocardial infarction (MI). Compared to non-diabetes, the risk of CVD and CKD increased in patients with diabetes. A meta-analysis including 102 studies showed that patients with diabetes had an overall risk of coronary heart disease (CHD) twice that of patients without diabetes. Except for the risk of CVD and CKD, clinical characteristics and treatment patterns may also differ among patients with or without diabetes. Studies showed diabetic patients may have a greater burden of other risk factors than nondiabetics, such as hypertension, hyperlipidemia, and obesity. Compared with individuals without diabetes, those with diabetes have a greater extent of coronary ischemia, and are more likely to have a MI and silent myocardial ischemia. Moreover, the effect of treatment on patients with or without diabetes may differ, thus the treatment patterns may be different.

China has the largest absolute disease burden of diabetes in the world recently. Diabetic patients with established CVD or CKD are bringing growing pressure upon our nation's healthcare expenditure. However, the characteristic profile of Chinese diabetic patients who has CVD, CKD or at high risk of CVD remains unclear thus is in urgent need for in-depth investigation. Several studies have shown that diabetes patients often suffer from multiple comorbidities, including the CV diseases, and clearly described the characteristics and treatment patterns of such patients. However, patient characteristics and treatment patterns

may differ across regions and hospitals. Lack of adequate understanding of such information may result in suboptimal management of patients and policy decisions. This is particularly true in China. In current China, however, the information regarding diabetes or non-diabetes patients who also had other comorbid conditions (e.g. established CV diseases, CKD or at high risk for such problem), is limited; the patient characteristics, treatment patterns and economic burden may not be fully understood. The treatment outcomes may be improved with better understanding about the current treatment pattern, patient characteristics, and potential treatment gap.

Regional medical data has received a lot of attention for its advantages on larger sample size and better representation of the general population. Tianjin regional database, which cover individual-level health information, is a valuable data source for clinical studies. Through integrating EMR systems of hospitals by patient unique identify code, the database contains comprehensive information regarding clinical care, such as patients' basic information, medical advice, diagnosis, laboratory examination, medical records and medical costs. It could be a valuable big data resource for clinical studies. Till now, data from 40 tertiary hospitals has been collected, and there were approximately 600,000 patients diagnosed with diabetes in these 40 tertiary hospitals from 01/01/2015 to 31/12/2019. Of these, 100,000 patients were with comprehensive information through integrating EMR systems. And Tianjin has built a unified medical purchasing center for hospitals to undertake joint procurement of medical supplies and drugs.

Therefore, based on Tianjin regional database, we will describe the demographic, clinical characteristics, treatment, and economic burden of disease of Chinese diabetic/non-diabetic patients with/without established CV disease, CKD, or at high CV risk including hypertension and hyperlipidemia. And we believe that the resulting findings will inform a comprehensive group of evidence users to achieve better healthcare for diabetes patients with established or at high risk of CVD or CKD.

## **8. RESEARCH QUESTION AND OBJECTIVES**

The study aims to investigate the clinical characteristics, treatment, and economic burden of disease of Chinese diabetic/non-diabetic patients with/without established cardiovascular disease, chronic kidney disease, or at high cardiovascular risk, including:

[figure not shown]
- Primary objectives: describe the proportion of Chinese diabetic/non-diabetic patients with established cardiovascular disease, CKD, or at high cardiovascular risk including hypertension and hyperlipidemia.
- Secondary objectives: describe the demographic characteristics of the last visit for all patients, and the demographic characteristics of inpatients over time; investigate the clinical characteristic for all patients.
- Further objectives: examine economic burden of disease of Chinese diabetic/non-diabetic patients with/without established cardiovascular disease, CKD, or at high cardiovascular risk; explore the trends of clinical characteristics, treatment patterns, economic burden of inpatients over time.

## **9. RESEARCH METHODS**

### **9.1 STUDY DESIGN**

This study is an observational, cross-sectional, study based on routinely-collected-data. We will use Tianjin regional medical database. It is conducted to investigate the clinical characteristics, treatment, and economic burden of disease of Chinese diabetic/non-diabetic patients with/without established cardiovascular disease, chronic kidney disease, or at high cardiovascular risk.

The study process is illustrated in figure 1.

## 9.2 SETTING

### 9.2.1 Study sites

This study is based on Tianjin regional database which is approved by Tianjin Municipal Health Commission and managed by [REDACTED], and authorized to [REDACTED] for this study use. It covers individual-level health information from 15 million residents in Tianjin. Till 2020, data from 40 tertiary hospitals has been collected, and we will use data from these 40 tertiary hospitals. The study was co-sponsored by [REDACTED] of the Health Data Special Committee of the [REDACTED], who was responsible for the research protocol design, as well as data cleaning, data analysis and final research report writing, and [REDACTED] of [REDACTED] as Co-PI who will be responsible for the research design.

### 9.2.2 Study population

Diabetic/non-diabetic patients with/without established cardiovascular disease, chronic kidney disease, or at high cardiovascular risk.

#### **Inclusion Criteria:**

- 1) Patients in the Tianjin regional database from 01/01/2015 to 31/12/2019.
- 2) Group A: patients with diagnosis of diabetes, and with diagnosis of cardiovascular disease, heart failure, chronic kidney disease or at high cardiovascular risk.
- 3) Group B: patients with diagnosis of diabetes, but not with diagnosis of cardiovascular disease, heart failure, chronic kidney disease or at high cardiovascular risk.
- 4) Group C: patients with diagnosis of cardiovascular disease, heart failure, chronic kidney disease or at high cardiovascular risk, but not with diagnosis of diabetes.
- 5) Group D: patients without diagnosis of cardiovascular disease, heart failure, chronic kidney disease or at high cardiovascular risk, and without diagnosis of diabetes. We will randomly select a group of non-diabetic patients without any of the above diseases by matching on age and gender.

Definition of diabetes, cardiovascular disease, chronic kidney disease and high cardiovascular risk:

- Diabetes: patients with at least 1 discharged diagnosis or 2 outpatient diagnosis of diabetes (the first diagnosis will be the index diagnosis, and the time interval between diagnoses is not restricted) (International classification of disease (ICD)-10 E10-E14)
- Cardiovascular disease: patients with at least 1 discharged diagnosis or 2 outpatient diagnosis of ischemic heart diseases (the first diagnosis will be the index diagnosis, and the time interval between diagnoses is not restricted) (ICD-10 I20~I25); or patients with at least 1 discharged diagnosis or 2 outpatient diagnosis of cerebrovascular diseases (the first diagnosis will be the index diagnosis, and the time interval between diagnoses is not restricted) (ICD-10 I60~I69); or patients with at least 1 discharged diagnosis or 2 outpatient diagnosis of ischemic peripheral artery disease (the first diagnosis will be the index diagnosis, and the time interval between diagnoses is not restricted) (ICD-10 E10.501, E11.603, E14.501, E14.606, E14.503, I73.9, I99.03, I99.04);

- Heart failure: patients with at least 1 discharged diagnosis or 2 outpatient diagnosis of heart failure (the first diagnosis will be the index diagnosis, and the time interval between diagnoses is not restricted) (ICD-10 I50).
- Chronic kidney disease: inpatients with at least once 1 discharged diagnosis CKD (ICD-10 N18), or inpatients with the last estimated glomerular filtration rate (eGFR, calculated by CKD-EPI equation) <60 mL/min/1.73 m^2 or prescription of dialysis, but not with the diagnosis of acute kidney injury (ICD-10 N17); or outpatients with at least 2 diagnosis of CKD (the first diagnosis will be the index diagnosis, and the time interval between diagnoses is not restricted) or with two consecutive eGFR (calculated by CKD-EPI equation) <60 mL/min/1.73 m^2 by 90 days or more.
- High cardiovascular risk: patients with at least 1 discharged diagnosis or 2 outpatient diagnosis of hypertension (the first diagnosis will be the index diagnosis, and the time interval between diagnoses is not restricted) (ICD-10 I10-I15); or at least 1 discharged diagnosis or 2 outpatient diagnosis of hyperlipidemia (ICD-10 E78.001-E78.003, E78.101, E78.203, E78.301-E78.304, E78.306, E78.401, E78.501, E78.902)

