**9.3.2.1 Primary outcomes**

1. The proportion of diabetic/non-diabetic patients with established cardiovascular disease, or chronic kidney disease, or at high cardiovascular risk.
2. The proportion of diabetic patients with established cardiovascular disease, or chronic kidney disease, or at high cardiovascular risk among all diabetic patients.
3. The proportion of non-diabetic patients with established cardiovascular disease, or chronic kidney disease, or at high cardiovascular risk among all non-diabetic patients.

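### One-contact outpatients enter the non-diabetic denominator of primary outcome 3 with almost no chance of meeting a disease rule, so its outpatient and pooled figures are not comparable with those for diabetic patients

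*Protocol*

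**What the plan says.** Protocol 9.2.2 opens the study to "Patients in the Tianjin regional database from 01/01/2015 to 31/12/2019". The exclusions cover only nationality and duplicate records. SAP 6.3 repeats both.

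Diabetes means "patients with at least 1 discharged diagnosis or 2 outpatient diagnosis of diabetes". Ischaemic heart disease, cerebrovascular disease, peripheral artery disease, heart failure and hyperlipidaemia have rules of the same form, as does hypertension: "patients with at least 1 discharged diagnosis or 2 outpatient diagnosis of hypertension". CKD can be met from one admission: "inpatients with at least once 1 discharged diagnosis CKD (ICD-10 N18), or inpatients with the last estimated glomerular filtration rate", or dialysis. An outpatient needs two CKD diagnoses, or two consecutive low eGFR values at least 90 days apart. For paired outpatient diagnoses the protocol adds that "the time interval between diagnoses is not restricted".

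Non-diabetic status has no definition of its own; it is failure to meet the diabetes rule. Primary outcome 3 (Protocol 9.3.2.1) is the proportion with CVD, CKD "or at high cardiovascular risk among all non-diabetic patients", and outcome 2 is the matching proportion among diabetic patients. SAP Table 1 shows outpatients and inpatients in separate columns, by year and overall. Group D is a 1:1 sample matched to Group A on age and gender (Protocol 9.3.1, SAP 6.1).

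**The concern.** The two denominators are built differently. Every diabetic outpatient has at least two recorded diagnoses, and so generally has enough contact to meet a second disease rule. A non-diabetic outpatient may have been seen once, for any reason. Such a patient enters the outcome 3 denominator as disease-free whatever the truth, and a person with diabetes seen once as an outpatient is counted there too.

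Outcomes 2 and 3 invite comparison. SAP 6.1 says the four groups are constructed for comparison, and SAP 10.1 plans two-sided tests at 0.05. Part of any diabetic excess in the outpatient or pooled figures could come from unequal opportunity to be classified, in the direction the protocol's rationale already expects.

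Nothing in the plan addresses this. Protocol 9.9 covers coding differences between hospitals and incomplete records. The 200-chart review checks the codes, not the opportunity to receive them. The ENCePP checklist answers No on analytic control of outcome misclassification.

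**Working it through.** The plan gives no expected proportion, precision or visit count, so there is no figure to reproduce. What follows illustrates the mechanism on assumed inputs.

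**1. Simple dilution.** Let *s* be the share of non-diabetic patients with one outpatient contact and no admission, and *p* the proportion who would qualify given enough contact. If *p* is the same in one-contact patients, the reported proportion is (1 − *s*)*p*. With *p* = 40%:
- *s* = 20%: 0.80 × 40% = 32%
- *s* = 35%: 0.65 × 40% = 26%
- *s* = 50%: 0.50 × 40% = 20%

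**2. Visit model with no true association, outpatients only.** Assumed inputs: diabetes in 20% and comorbidity in 40%, independent of each other and of visits; visits *k* geometric, w(k) = a(1 − a)^(k−1), where a is the single-visit share; each condition coded at a visit with probability *q*. The chance of meeting a two-diagnosis rule is t(k) = P(Binomial(k, q) ≥ 2), so t(1) = 0.
- Diabetic: 0.4 × Σw·t² / Σw·t
- Non-diabetic: 0.4 × Σw(1 − 0.2t)t / Σw(1 − 0.2t)
- With a floor of two visits, the sums start at k = 2. The diabetic figure does not change, because t(1) = 0.

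Results from a simulation of 2,000,000 patients; summing the formulas directly agrees within 0.2 points:

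| Single-visit share | Coding per visit | Diabetic | Non-diabetic, as written | Gap (points) | Non-diabetic, with floor | Gap (points) |
|---|---|---|---|---|---|---|
| 30% | 60% | 31.3% | 18.2% | 13.1 | 27.2% | 4.1 |
| 30% | 80% | 35.5% | 22.6% | 12.9 | 34.4% | 1.1 |
| 50% | 60% | 26.1% | 10.3% | 15.8 | 22.0% | 4.1 |
| 50% | 80% | 32.8% | 14.3% | 18.5 | 31.3% | 1.5 |

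The true gap is zero in every row.

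**3. A second visit pattern.** Assumed: true proportion 60% in both groups, diabetes share 15%, perfect coding, share *s* seen once and the rest split evenly over 2, 3, 4 and 6 visits. The non-diabetic figure is 0.60 × 0.85(1 − s) / [s + 0.85(1 − s)]. For s = 0.2 this is 0.408/0.88 = 46.4% against 60.0%, a false gap of 13.6 points. For s = 0.4 and 0.6 the gaps are 26.4 and 38.3 points. With the floor all three are zero. At 70% coding the gaps are 13.6, 23.5 and 32.9 points as written, and 3.1 with the floor.

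**4. Inpatients.** With inpatients only, the same method gives no gap (54.0% in both groups at 90% coding per admission), because one discharge is enough. Adding 20% inpatients to the model in step 2 at 80% outpatient coding gives 35.8% v 25.1% (30% single-visit) and 34.0% v 18.3% (50%). With the floor the non-diabetic figures become 34.8% and 32.9%. Pooling dilutes the artefact but does not remove it.

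**5. Which denominator.** If outcome 3 were computed on Group C plus the sampled Group D, D would be fixed at the size of A, and the result would be C/(C + A). With illustrative sizes C = 1,000,000 and A = 480,000 this is 1,000,000/1,480,000 = 67.6% whatever *s* is. One-contact patients would not lower it, but it would not be a proportion among all non-diabetic patients either.

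**The case against.** Several counter-arguments have force.

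- A reader might infer that all one-visit patients, and outcome 3 as a whole, are affected. The documents do not support that. A single admission can meet every rule, and SAP Table 1 keeps the settings apart.
- A reader might infer that one-contact outpatients can never qualify. The protocol does not expressly require the two outpatient diagnoses to come from separate visits, so two codes at one visit might be counted. Almost never is the most that can be said.
- A reader might infer that the contrast is always inflated. The models assume that visit counts do not depend on disease. There is also an opposing force: a patient with one outpatient diabetes code and two hypertension codes falls into Group C and raises outcome 3.
- The floor can itself mislead. Let p1 and p2 be the true proportions in single-visit and multi-visit non-diabetic patients. The rule as written understates the overall proportion by s·p1; the floor overstates it by s(p2 − p1), which is larger when p1 < p2/2. With assumed s = 35%, p2 = 40% and p1 = 10%, the truth is 0.65 × 40% + 0.35 × 10% = 29.5%, against 26% as written and 40% with the floor. This stands as a reason to report both figures. It does not rescue the comparison, because the diabetic figure already describes only patients with repeat contact or an admission.
- The study is descriptive. The ENCePP checklist marks measures of association and hypotheses as not applicable, and Table 1 has no test column. This limits the consequence, but SAP 6.1 and 10.1 still provide for comparison and testing.

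**Conclusion.** The concern holds for the outpatient columns of SAP Table 1 and for any figure pooling outpatients with inpatients, provided the outcome 3 denominator is what Protocol 9.3.2.1 says, all non-diabetic patients. The 1:1 sampling of Group D leaves some doubt about that, because neither document says which set Table 1 uses. The inpatient columns are not affected by this mechanism.

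The asymmetry can be read directly from the text; its size cannot. With 30–50% single-visit patients and 60–80% coding per visit, the false gap is about 13 to 19 points, and about 1 to 4 remain with a common floor. These are not bounds: the second visit pattern, with perfect coding and up to 60% seen once, reaches 38. All visit distributions, coding rates and prevalences are assumptions. The point should be settled before extraction because it bears on a primary outcome and is cheap to address.

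**What to change.** In Protocol 9.2.2 and 9.3.2.1 and SAP 6.3 and 7.2.1:

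1. State that the outcome 3 denominator is all eligible non-diabetic patients, not Group C plus the sampled Group D.
2. For the outpatient columns and any pooled figure, report outcomes 1–3 twice: unrestricted, and restricted to patients with at least one discharge or at least two outpatient visits between 01/01/2015 and 31/12/2019. Apply the restriction alike to diabetic and non-diabetic patients and to the pool from which Group D is drawn.
3. Use the restricted figures for any diabetic versus non-diabetic comparison, and report how many patients the restriction removes from each group.

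The cost is a few sentences in each document, one filter at extraction and a second set of outpatient and pooled figures. Few diabetic patients should be lost, since nearly all already meet the floor; the exception would be someone with two codes from a single visit.

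The restricted result describes only patients with enough contact to be classified. It may overstate the proportion among all non-diabetic attenders if single-visit patients are healthier. A five-year floor does not fully equalise the annual columns or the 90-day eGFR rule, and a small gap remains where coding is incomplete. The report should say so.

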**9.3 VARIABLES**

The following variables will be collected in this study.

- 1) Demographic characteristics of the patients: age, gender, type of health insurance, etc.
- 2) Status of the patient's disease diagnosis: outpatient diagnosis, discharge diagnosis.
- 3) Information on the patient's laboratory tests, glycated haemoglobin, blood glucose, blood creatinine, estimated glomerular filtration rate, urine microalbumin, lipids, etc.
- 4) Patient medication and treatment: including CVD-related treatment (antiplatelet agents, statins, vasodilators), diabetes-related treatment (insulin, oral hypoglycaemic agents),

hypertension-related treatment (e.g. calcium antagonists, angiotensin-converting enzyme antagonists, angiotensin receptor antagonists, beta-receptor antagonists, etc.), hyperlipidaemia-related treatment (e.g. lipid-lowering drugs), CKD-related treatment (e.g., dialysis, angiotensin-converting enzyme antagonists, angiotensin receptor antagonists, kidney transplantation), etc.

- 5) Number of days the patient was hospitalized
- 6) Patient's medical costs, including all costs during hospitalization (hospitalization, drugs, surgery, etc.)

Table 1. variables collected from database

Table Name	Variables
Basic information	medical organization
	unique ID of patients
	birthday
	sex
	ethic
	type of insurance
Laboratory	unique ID of patients
	report number
	test date
	test time
	item test name
	item test result
	item test unit
	item test sample
item test range	
Diagnosis	unique ID of patients
	diagnosis
	admission status
	discharge status
	diagnosis date
	department
Advice	unique ID of patients
	advice item name
	dose per time

	total dose
	unit of dosage
	frequency
	advice start date
	advice stop date
Front sheet	unique ID of patients
	admission department
	admission date
	discharge department
	discharge date
	length of hospital stay
	discharge way
Fee information	unique ID of patients
	fee item name
	unit price
	quantity
	total price
	charge date

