**9.3.1 Exposures**

Not applicable.

We defined four groups (group A-D) according to the diagnosis and laboratory measurements. The group A and group B included all diabetic patients with/without established CV disease, CKD, or at high CV risk, respectively. The group C included all non-diabetic patients with established cardiovascular disease, chronic kidney disease, or at high cardiovascular risk. The group D included non-diabetic patients without established cardiovascular disease, chronic kidney disease, and not at high cardiovascular risk. For group D, we will randomly sample study populations to acquire a 1:1 sample of non-diabetic patients without disease by matching on age and gender with group A.

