6.3 STUDY POPULATION

Diabetic/non-diabetic patients with/without established cardiovascular disease, chronic kidney disease, or at high cardiovascular risk.

Inclusion Criteria:

- 1) Patients in the Tianjin regional database from 01/01/2015 to 31/12/2019.
- 2) Group A: patients with diagnosis of diabetes, and with diagnosis of cardiovascular disease, heart failure, chronic kidney disease or at high cardiovascular risk;
- 3) Group B: patients with diagnosis of diabetes, but not with diagnosis of cardiovascular disease, heart failure, chronic kidney disease or at high cardiovascular risk;
- 4) Group C: patients with diagnosis of cardiovascular disease, heart failure, chronic kidney disease or at high cardiovascular risk, but not with diagnosis of diabetes;
- 5) Group D: patients without diagnosis of cardiovascular disease, heart failure, chronic kidney disease or at high cardiovascular risk, and without diagnosis of diabetes. We will randomly select a group of non-diabetic patients without any of the above diseases by matching on age and gender.

Definition of diabetes, cardiovascular disease, chronic kidney disease and high cardiovascular risk

- Diabetes: patients with at least 1 discharged diagnosis or 2 outpatient diagnosis of diabetes (ICD-10 E10-E14)
- Cardiovascular disease: patients with at least 1 discharged diagnosis or 2 outpatient diagnosis of ischemic heart diseases (ICD-10 I20~I25); or patients with at least 1 discharged diagnosis or 2 outpatient diagnosis of cerebrovascular diseases (ICD-10 I60~I69); or patients with at least 1 discharged diagnosis or 2 outpatient diagnosis of ischemic peripheral artery disease (ICD-10 E10.501, E11.603, E14.501, E14.606, E14.503, I73.9, I99.03, I99.04);
- Heart failure: patients with at least 1 discharged diagnosis or 2 outpatient diagnosis of heart failure (ICD-10 I50);
- Chronic kidney disease: inpatients with at least once 1 discharged diagnosis CKD (ICD-10 N18), or inpatients with the last estimated glomerular filtration rate (eGFR, calculated by CKD-EPI equation) <60 mL/min/1.73 m² or prescription of dialysis, but not with the diagnosis of acute kidney injury (ICD-10 N17); or outpatients with at least 2 diagnosis of CKD or with two consecutive eGFR (calculated by CKD-EPI equation) <60 mL/min/1.73 m² by 90 days or more.

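### Diabetes is identified by ICD-10 codes alone; a sensitivity analysis on HbA1c and treatment data already being extracted would show how many uncoded diabetics sit in Groups C and D

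*Protocol*

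**What the plan says.** The diabetes rule is the same in both documents and uses codes only. Protocol 9.2.2 reads "Diabetes: patients with at least 1 discharged diagnosis or 2 outpatient diagnosis of diabetes", with the range E10-E14, and SAP 6.3 agrees: "Diabetes: patients with at least 1 discharged diagnosis or 2 outpatient diagnosis of diabetes (ICD-10 E10-E14". Neither gives a laboratory or medication route.

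Non-diabetic status is the absence of that diagnosis. Group C is defined by "chronic kidney disease or at high cardiovascular risk, but not with diagnosis of diabetes". Group D has none of the listed conditions "and without diagnosis of diabetes".

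Protocol 9.3 puts the data that could reveal uncoded diabetes on the extraction list: "Information on the patient's laboratory tests, glycated haemoglobin, blood glucose" and "diabetes-related treatment (insulin, oral hypoglycaemic agents". Its Table 1 gives the Advice file an item name, doses, and start and stop dates, and the Front sheet file admission and discharge dates. SAP Table 4 reports HbA1c and random glucose for all four groups.

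CKD is handled differently. Besides codes, the rule accepts "inpatients with the last estimated glomerular filtration rate (eGFR, calculated by CKD-EPI equation" below 60, or a dialysis prescription, provided there is no acute kidney injury diagnosis. For outpatients it accepts two consecutive low values at least 90 days apart.

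The one planned check on the codes is a review of 200 randomly selected charts. Protocol 9.7.1 includes type 2 diabetes in it. SAP 11 names only cardiovascular disease and high cardiovascular risk.

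**The concern.** Diabetic status is the main axis of the study. It sets numerator and denominator of primary outcomes 2 and 3, and it labels every column of the descriptive tables. An uncoded diabetic is placed on the wrong side of that axis, and the plan has no step that would notice.

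The error is unlikely to be neutral. Protocol 7 says that diabetes raises the risk of CVD and CKD. If that also holds for uncoded diabetics, they raise the disease/risk proportion among non-diabetics, narrow the contrast with diabetics, and lift HbA1c and glucose in the Group C and D columns. Protocol 9.9 concedes that hospitals may understand ICD codes differently, so the share of uncoded diabetics may also vary by hospital.

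**Working it through.** The documents give no sensitivity for the diabetes codes, no share of uncoded diabetics and no count of non-diabetic patients. There is no plan figure to reproduce. The numbers below are illustrations, and every input marked as assumed is an assumption.

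**1. Trace one patient through the rules.** Take an outpatient with no E10-E14 code, a clearly diabetic HbA1c, and two eGFR values below 60 taken 90 days apart. The laboratory route makes the patient CKD. No route makes the patient diabetic. The patient enters Group C, counts in numerator and denominator of primary outcome 3, and has the HbA1c shown in a non-diabetic column of SAP Table 4. The same patient with normal eGFR and no other qualifying condition is eligible for Group D.

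**2. Shift in primary outcome 3.** Let q be the share of uncoded diabetics among all labelled non-diabetics (assumed 1-10%). Let pN be the disease/risk proportion in true non-diabetics (assumed 0.40 or 0.60) and pU that in uncoded diabetics (assumed 0.80).

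Observed proportion = pN + q × (pU − pN), so the shift is q × (pU − pN).

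| q | gap 20 points (0.80 v 0.60) | gap 40 points (0.80 v 0.40) |
|---|---|---|
| 1% | 0.2 | 0.4 |
| 3% | 0.6 | 1.2 |
| 5% | 1.0 | 2.0 |
| 10% | 2.0 | 4.0 |

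Shifts are in percentage points. For scale, with an assumed 100,000 non-diabetics and a proportion of 0.40, the 95% half-width is 1.96 × √(0.40 × 0.60 / 100,000) = 0.0030, or 0.3 points. In a database of that size, most of the table exceeds sampling error.

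**3. Shift in HbA1c (SAP Table 4).** Let s be the share of uncoded diabetics among HbA1c-tested patients in a column, and assume a mean gap of 2.0 HbA1c points. The shift is 2.0 × s: 0.02, 0.06, 0.10 and 0.20 for s = 1%, 3%, 5% and 10%. In Group C, s can exceed q, because patients with more disease fall into C. At q = 5%, pU = 0.80 and pN = 0.40, the uncoded share of Group C is 0.05 × 0.80 / 0.42 = 9.5%, before any effect of selective testing.

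**4. What the chart review could show.** Even if all 200 charts came from labelled non-diabetics, the expected number of uncoded diabetics is 200 × q: 2, 6, 10 or 20 for q = 1%, 3%, 5% or 10%. If instead all 200 informed one estimate of code sensitivity, the 95% half-width, 1.96 × √(p(1 − p)/200), would be 3.0 points at 0.95 and 6.4 points at 0.70. It is wider if the charts are shared among conditions. The review could reveal a large problem, but it moves nobody between groups.

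**5. Data coverage.** Comprehensive records are stated for 100,000 of 600,000 diabetic patients in the Protocol (16.7%) and for 10,000 in SAP 8 (1.7%). Nothing is stated for non-diabetics. Any count based on laboratory values or orders is therefore a minimum.

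**The case against.** The strongest reply is that the groups are meant to reflect diagnosed diabetes. The inclusion criteria speak of diagnosis throughout, and the row labels of SAP Table 1 do the same. CVD, heart failure, hypertension and hyperlipidaemia are also code-only, so CKD is the exception. This stands: the definition is a legitimate choice and need not change.

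A reader might infer a contradiction from Protocol 9.3.1, which says "We defined four groups (group A-D) according to the diagnosis and laboratory measurements". The documents do not support that. CKD status helps to separate A from B and C from D, and it uses eGFR, so the sentence is true without any laboratory criterion for diabetes.

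A reader might also infer that nothing checks the diabetes codes. Protocol 9.7.1 does plan a check. What remains is that SAP 11 leaves diabetes out of it, and that neither document says what follows if the codes perform poorly.

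The magnitude is assumed throughout. Patients with no diabetes code may have few hospital contacts and so few other codes, which would shrink the gap. That is fair, and it is a reason to count them.

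Finally, a flag has practical limits. Testing is selective, the Advice file has no field for care setting, and Group D is matched 1:1 to Group A. The fix has to deal with each.

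**Conclusion.** The point holds as a cheap improvement. The plan's definition contains no error, but patients without a diabetes code count as non-diabetic whatever their HbA1c or treatment, and no step in the available text counts or reclassifies them. The ENCePP checklist answers No on information bias (7.3) and on control of outcome misclassification (10.6). It cites Protocol 9.7.1 for sensitivity analyses (10.8), but that section describes none. Protocol 9.7.2 and SAP 10.2 are not in the public copy, so an analysis placed there cannot be excluded.

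Under the assumptions above, primary outcome 3 would rise by about 0.2 to 4 points. The upward direction assumes that uncoded diabetics have more disease/risk than true non-diabetics. Protocol 7 supports this for diabetics in general but not for uncoded ones specifically. A reader might conclude that primary outcome 3 is known to be materially biased; the documents give no figure from which that could be shown. The point concerns patients with no E10-E14 code at all. Those with a single outpatient code are a separate matter.

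**What to change.** Keep the main definition and add one pre-specified sensitivity analysis to SAP 10.

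- **Flag.** Mark patients without any E10-E14 code who have either an HbA1c at or above a cut-off fixed in advance by the clinical team, or a glucose-lowering order (oral agent or insulin) dated outside any admission. Derive the second condition by comparing advice dates with front-sheet admission and discharge dates, and state how an order dated on the day of discharge is treated. Insulin given only during an admission then does not count.
- **Timing.** Apply the flag to the whole non-diabetic pool before Group D is drawn, or re-match D to A afterwards.
- **Output.** Repeat SAP Tables 1 and 4 twice: with flagged patients excluded from C and D, then with them counted as diabetic. Report the number flagged, and the number in each group with HbA1c and with order data.
- **Chart review.** Add diabetes to the review in SAP 11, in line with Protocol 9.7.1.

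The cost is one derived flag, two repeats of two tables, and a new draw of Group D, because counting flagged patients as diabetic enlarges Group A. The limits should be stated with the result: the count is a minimum, since laboratory data are partial and testing is selective, and a few patients taking these drugs for other reasons will be flagged.
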